12.4 Analysis of the primary endpoint(s)

12.4.1 Definition of primary endpoint(s)

The primary efficacy endpoint in the study is change in total PANSS score from baseline to day 85 or last visit, analyzed using the FAS.

12.4.2 Statistical model, hypothesis, and method of analysis

The change from baseline in total PANSS score will be analyzed using the mixed-effects model for repeated measures (MMRM) [Mallinckrodt et al 2001](#), including the fixed, categorical effects of treatment, visit, and treatment-by-visit interaction, as well as the continuous, fixed covariates of baseline score, baseline score-by-visit interaction, and disease duration at baseline. An unstructured (UN) covariance structure will be used to model the within-patient errors. The Kenward-Roger (KR) method will be used to adjust the estimated covariance of the mean difference and the degrees of freedom.

Corporate Confidential Information

12.4.3 Handling of missing values/censoring/discontinuations

The primary MMRM model implicitly imputes missing data under a missing at random (MAR) assumption. Therefore, no explicit imputation of missing data will be done for the primary analysis approach.

12.4.4 Sensitivity and Supportive analyses

12.4.4.1 Sensitivity analyses

Two sensitivity analyses to assess the robustness of the primary analysis to missing data results will be performed.

Corporate Confidential Information

12.4.4.2 Supportive analyses

The last-observation-carried-forward (LOCF) approach will be applied to analyze the change from baseline in the total PANSS score. These results will only be used to aid in the interpretation of the results from the primary analysis.

12.5 Analysis of secondary endpoints

12.5.1 Efficacy endpoint(s)

The secondary efficacy endpoints listed below will be analyzed separately using an MMRM analysis. The change from baseline to each post-baseline visit will be the dependent variable. The model will include the fixed, categorical effects of treatment, visit, and treatment-by-visit interaction, as well as the continuous, fixed covariates of baseline score, baseline score-by-visit interaction, and disease duration at baseline (in years). The analysis strategy will be the same as for the primary outcome ([Section 12.4.2](#)). The outcomes to be analyzed are:

- change from baseline in the positive PANSS score;
- change from baseline in the General Psychopathology PANSS score;
- change from baseline in the negative PANSS score;
- change from baseline in the MAP-SR score;
- change from baseline in the WHOQOL-BREF scale;
- change from baseline in the BDI-II total score

In addition, the percentage change from baseline in the total PANSS score will be analyzed using an MMRM approach, as described in [Section 12.4.2](#). Estimates of mean percentage change from baseline to each study visit with (90% CIs) will be obtained for each treatment group.

Corporate Confidential Information

12.5.2 Safety endpoints

For all safety analyses, the safety set will be used. All listings and tables will be presented by treatment group.

Safety summaries (tables, figures) include only data from the on-treatment period with the exception of baseline data which will also be summarized where appropriate (e.g. change from baseline summaries). In addition, a separate summary for death including on treatment and post treatment deaths will be provided. In particular, summary tables for adverse events (AEs) will summarize only on-treatment events, with a start date during the on-treatment period (**treatment-emergent** AEs).

The on-treatment period lasts from the date of first administration of study treatment to 30 days after the date of the last actual administration of any study treatment.

Adverse events

All information obtained on AEs will be displayed by treatment group and subject.

The number (and percentage) of subjects with AEs will be summarized in the following ways:

- by treatment, primary system organ class and preferred term.
- by treatment, primary system organ class, preferred term and maximum severity.

Separate summaries will be provided for study medication related AEs, death, SAEs, and other significant AEs leading to discontinuation.

A subject with multiple AEs within a primary system organ class is only counted once towards the total of the primary system organ class.

Vital signs

All vital signs data will be listed by treatment group, subject, and visit/time and if ranges are available, abnormalities as well as clinically notable values will be flagged. Summary statistics will be provided by treatment and visit/time.

Other safety evaluations

ISST-Plus score data will be listed by treatment, subject and visit/time; abnormalities will be flagged. Summary statistics will be provided by treatment and visit/time as appropriate.

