
 • To evaluate the efficacy of PEAR-004 as an adjunct to existing clinician-directed pharmacotherapy to improve psychosocial functioning in patients with schizophrenia 	
 • Change on the World Health Organization Quality of Life (WHOQOL-BREF) scale from baseline to day 29, day 57, and day 85 or last visit

 • To evaluate the efficacy of PEAR-004 as an adjunct to existing clinician-directed pharmacotherapy to reduce depression symptoms in patients with schizophrenia 	
 • Change in the Beck Depression Inventory, Second Edition (BDI-II) total score from baseline to day 29, day 57, and day 85 or last visit

 • To evaluate the magnitude of the effect of PEAR-004 as an adjunct to existing clinician-directed pharmacotherapy to reduce symptoms of schizophrenia 	
 • Percentage change in PANSS score (within assigned group) from baseline to day 29, day 57, and day 85 or last visit

 • To evaluate the response to treatment 	
 • Proportion of responders, defined as a reduction of at least 20% at day 85 or last visit in total PANSS score relative to baseline

 • To evaluate patient adherence to antipsychotic medication 	
 • Change in antipsychotic pharmacotherapy use as measured by the Brief Medication Questionnaire (BMQ) at day 29, day 57, and day 85 or last visit

Exploratory Objectives

Corporate Confidential Information

Corporate Confidential Information

3 Study design

This is a randomized, sham controlled, rater-blinded, parallel group trial. Approximately 102 subjects will be randomized 1:1 in to the following groups:

- Group A: Clinician-directed pharmacotherapy + PEAR-004
- Group B: Clinician-directed pharmacotherapy + Sham application

An up to 28-day screening period will include standard screening assessments as defined in the assessment schedule. Eligible subjects will be randomized on day 1 into one of the treatment groups.

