Conditions that were already present at the time of informed consent should be recorded in medical history of the subject.

Adverse events should be described using a diagnosis whenever possible, rather than individual underlying signs and symptoms.

Once an adverse event is detected, it must be followed until its resolution or until it is judged to be permanent (e.g. continuing at the end of the study), and assessment must be made at each visit (or more frequently, if necessary) of any changes in severity, the suspected relationship to the interventions required to treat it, and the outcome.

Follow the instructions found in the Site Operations Manual for data capture methodology regarding AE collection for subjects that fail screening.

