10.1.2 Serious adverse events

An SAE is defined as any adverse event [appearance of (or worsening of any pre-existing)] undesirable sign(s), symptom(s) or medical conditions(s)) which meets any one of the following criteria:

- fatal
- life-threatening
 - Life-threatening in the context of a SAE refers to a reaction in which the subject was at risk of death at the time of the reaction; it does not refer to a reaction that

hypothetically might have caused death if it were more severe (please refer to the ICH-E2D Guidelines).

- results in persistent or significant disability/incapacity
- constitutes a congenital anomaly/birth defect
- requires inpatient hospitalization or prolongation of existing hospitalization, unless hospitalization is for:
 - routine treatment or monitoring of the studied indication, not associated with any deterioration in condition
 - elective or pre-planned treatment for a pre-existing condition that is unrelated to the indication under study and has not worsened since signing the informed consent
 - social reasons and respite care in the absence of any deterioration in the subject's general condition
 - treatment on an emergency outpatient basis for an event not fulfilling any of the definitions of a SAE given above and not resulting in hospital admission
- is medically significant, e.g. defined as an event that jeopardizes the subject or may require medical or surgical intervention to prevent one of the outcomes listed above

Medical and scientific judgment should be exercised in deciding whether other situations should be considered serious reactions, such as important medical events that might not be immediately life threatening or result in death or hospitalization but might jeopardize the subject or might require intervention to prevent one of the other outcomes listed above. Such events should be considered as “medically significant”. Examples of such events are intensive treatment in an emergency room or at home for allergic bronchospasm, blood dyscrasias or convulsions that do not result in hospitalization or development of dependency or abuse.

All malignant neoplasms will be assessed as serious under “medically significant” if other seriousness criteria are not met.

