6.3 Exploratory objectives

Corporate Confidential Information

7 Statistical methods for safety and tolerability data

For all safety analyses, the safety set will be used. All listings and tables will be presented by treatment group. Safety summaries (tables, figures) include only data from the on-treatment period with the exception of baseline data which will also be summarized where appropriate (e.g. change from baseline summaries). In addition, a separate summary for death including on treatment and post treatment deaths will be provided. In particular, summary tables for

adverse events (AEs) will summarize only on-treatment events, with a start date during the on-treatment period (**treatment-emergent** AEs).

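### Treatment-emergent AEs are defined by start date alone, so an AE that begins in screening and worsens on treatment is missing from most AE summaries unless the worsening is recorded as a new event

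*Protocol*

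**What the plan says.** Protocol 12.5.2 sets a general limit: "Safety summaries (tables, figures) include only data from the on-treatment period with the exception of baseline data". For AEs it then selects on onset: "summary tables for adverse events (AEs) will summarize only on-treatment events, with a start date during the on-treatment period". The window is also defined there: "The on-treatment period lasts from the date of first administration of study treatment to 30 days after the date of the last actual administration". SAP section 7 carries the same selection rule, namely that AE tables "will summarize only on-treatment events, with a start date during the on-treatment period". Neither document adds a clause for worsening.

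Collection starts earlier than the window. Protocol 10.1.1 defines an AE as an untoward occurrence after written consent, and Table 8-1 schedules AE recording at screening. On the length of screening, protocol section 3 says: "An up to 28-day screening period will include standard screening assessments as defined in the assessment schedule". Conditions already present at consent go to medical history. Once an AE is detected it is followed to resolution or permanence, and "assessment must be made at each visit (or more frequently, if necessary) of any changes in severity". The SAE definition in 10.1.2 opens with "appearance of (or worsening of any pre-existing", so it takes in worsening as well as new onset.

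Two outputs in 12.5.2 are not tied to AE start date: a separate summary of on-treatment and post-treatment deaths, and a display of all AE information by subject.

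**The concern.** The selection rule looks only at when an event began. The protocol's follow-up and SAE rules also look at what happens to it later. An AE that opens as mild between consent and day 1 and becomes severe or serious while the subject is using the app is, for safety purposes, an on-treatment change. With its screening start date it fails the filter.

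Table 2-1 defines the safety endpoint as AEs, SAEs and AEs leading to discontinuation across the whole study. Under the start-date rule, the summary tables that serve this endpoint could omit an on-treatment deterioration, including one reportable as an SAE. A reader of the tables would not know that it had been left out.

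**Working it through.** The plan states no figure on this point, so there is none to reproduce. The check applies the written rule to example events and then considers size.

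**Step 1: the window.** It runs from first administration (day 1) to last administration plus 30 days. With last use on day 85, 85 + 30 = 115, so the window is day 1 to day 115. An AE is tabulated if 1 ≤ start day ≤ 115.

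**Step 2: which events can start before it.** AEs are recorded from consent, and Table 8-1 places screening on days -28 to -1. An AE with a start day in that range is therefore possible.

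**Step 3: apply the rule.**

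| Example event | Start day(s) on record | In AE tables? |
|---|---|---|
| Starts day -14, worsens day 20, one record | -14 | No |
| Starts day -14, becomes serious day 20, one record | -14 | No |
| Starts day -14, worsening on day 20 entered as a new record | -14 and 20 | Yes, through the second record |
| Starts day 20 | 20 | Yes |
| Starts day 110 | 110 | Yes |

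**Step 4: which outputs are affected.** For the first two rows, the event is absent from the summaries by system organ class and preferred term and by maximum severity. It is also absent from those of related AEs, SAEs and AEs leading to discontinuation, because 12.5.2 exempts none of these. It stays in the by-subject display. If it is fatal, the death appears in the death summary, which goes by when the death occurs.

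**Step 5: does the text settle how worsening is recorded?** Protocol 10.1.1 asks for a severity grade and for start and end dates, and for severity changes to be assessed at each visit. It says neither that a worsening stays on the original record nor that it opens a new one. The result therefore depends on a convention that the two documents do not fix.

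**Step 6: size.** The documents give no AE rates, so the number affected cannot be computed. Screening is at most 28 of 28 + 84 + 30 = 142 days of AE collection: 28/142 = 0.197, or about 20%. With 102/2 = 51 subjects per arm, one subject is 1/51 = 2.0 percentage points. Purely as an illustration, suppose a share p of subjects have a screening-onset AE open on day 1, a share q of those worsen on treatment, and every worsening stays on one record. The number affected per arm is then 51 × p × q:

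- p = q = 0.10: 51 × 0.10 × 0.10 = 0.5
- p = q = 0.20: 51 × 0.20 × 0.20 = 2.0
- p = q = 0.30: 51 × 0.30 × 0.30 = 4.6

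The shares are assumptions with no basis in the documents. Because the event must both begin within 28 days at most and still be open on day 1, the lower end is more plausible.

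**The case against.** The strongest objection is that the omission may never occur. The SAP's rule for the registry tables (section 7.2, Adverse events) merges consecutive records with the same system organ class and preferred term when the gap is at most 1 day, whatever their severity or seriousness. It counts a block as an SAE occurrence if any record in it is serious. That rule fits a database in which a worsening opens a new record. The SAE definition also allows the worsening itself to be the event, with its own on-treatment onset. Detailed recording instructions are in the Site Operations Manual, which is not among these documents.

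This stands as a limit: the loss is conditional. It does not remove the point. A rule for counting consecutive records is not an instruction to create them, and such records can also come from recurrence. The merge rule covers only the registry tables and does not say how a block that begins before first administration is dated.

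A reader might infer two stronger claims. The first is that such events vanish from every AE summary. The death summary contradicts that, and the by-subject display, though not a summary table, keeps the record. The second is that worsening of long-standing schizophrenia symptoms goes uncounted. The documents do not support this either. Symptoms present at consent go to medical history, so a later worsening reported as an AE would start on treatment and be tabulated. PANSS, BDI-II and ISST-Plus also track symptoms, depression and suicidality at each treatment visit. They do not replace AE tables, but they narrow what could be missed.

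**Conclusion.** The point holds in conditional form. Both documents define treatment-emergent AEs by start date only. Unless worsening is recorded as a new event, an AE that begins between consent and day 1 and then worsens, becomes serious or leads to discontinuation on treatment is missing from the AE summaries other than the death summary. This is a gap in a stated rule, because nothing in the protocol or SAP requires the recording practice that would close it.

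The effect is probably small. The affected events must begin in at most 28 days, remain open at day 1, worsen afterwards and be kept on one record. The rule is the same in both arms, and the primary efficacy analysis is untouched. It is still worth correcting, since the change is simple and one subject moves an arm's incidence by about 2 percentage points.

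**What to change.** In protocol 12.5.2 and SAP section 7, define a treatment-emergent AE as one that starts on or after first administration within the on-treatment period, or one that was present before first administration and increases in severity or becomes serious during that period. Then:

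- State that such worsening is recorded with its own date, or as a new record, and put this in the eCRF completion instructions.
- Apply the definition to all AE and SAE tables, including the registry tables in SAP 7.2.
- Say how the 1-day-gap rule dates and counts a block that straddles first administration.
- Say how the discontinuation summary treats a screening-onset AE that leads to stopping without a rise in severity or seriousness, since the extended definition alone would not capture it.

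The cost is a few sentences in two documents and one eCRF instruction. The only downside is slightly higher AE counts in both arms.

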1.2 Purpose

The purpose of the study is to determine in patients currently being administered antipsychotic pharmacotherapy whether PEAR-004 can further reduce symptoms of schizophrenia as measured by the total score on the Positive and Negative Syndrome Scale (PANSS).

2 Objectives and endpoints

Table 2-1 Objectives and related endpoints

Objectives and endpoints	
Primary Objective	
Objective	Endpoint

 To assess the efficacy of PEAR-004 as an adjunct to existing clinician-directed pharmacotherapy to reduce symptoms of schizophrenia 	
 Change in total PANSS score from baseline to day 85 or last visit

 To evaluate retention to assigned study treatment 	
 Percent dropout rate
Secondary Objectives	
Objectives	Endpoints

 To evaluate the efficacy of PEAR-004 as an adjunct to existing clinician-directed pharmacotherapy to reduce positive symptoms of schizophrenia 	
 Change in the Positive PANSS score from baseline to day 29, day 57, and day 85 or last visit Change in the General Psychopathology PANSS score from baseline to day 29, day 57 and day 85 or last visit

 To evaluate the efficacy of PEAR-004 as an adjunct to existing clinician-directed pharmacotherapy to reduce negative symptoms of schizophrenia 	
 Change in the Negative PANSS score from baseline to day 29, day 57, and day 85 or last visit Change in the Motivation and Pleasure self-report (MAP-SR) score from baseline to day 29, day 57, and day 85 or last visit

 To assess safety and tolerability of PEAR-004 	
 Adverse events, serious adverse events, and adverse events leading to discontinuation throughout the study

	
 • Vital signs at baseline, day 85 or last visit • InterSePT Scale for Suicidal Thinking-Plus (ISST-Plus) score at baseline, day 29, day 57, day 85, and day 115 or last visit

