6.1 Study treatment

Details on the requirements for management of study treatment, and instructions to be followed for subject numbering, providing and utilizing study treatment are outlined in the SOM.

PEAR-004 is an investigational digital therapeutic, currently available on a mobile device (iOS and Android based). It is designed to serve as an illness self-management tool. Subjects can

access PEAR-004 as needed to receive suggestions about coping strategies to overcome difficulties in daily life.

A control sham will be available to the control group. The sham will be downloaded to the subject's phone, but will not deliver the active therapeutic content of PEAR-004. It will deliver notifications prompting the subject to open the sham app, and will then display a prescription timer for the remaining duration of app availability.

Eligible subjects will gain access to either PEAR-004 or sham according to their randomization assignment via a digital prescription access code provided to the site. Study site staff will receive training on how to download PEAR-004 or sham to the assigned subject's phone as part of site initiation activities.

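### The safety summaries stop 30 days after an undefined last administration, which conflicts with the day-115 ISST-Plus endpoint and with follow-up of subjects who stop treatment

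*Protocol*

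**What the plan says.** Protocol 12.5.2 restricts the summaries: "Safety summaries (tables, figures) include only data from the on-treatment period with the exception of baseline data". It then defines the period: "The on-treatment period lasts from the date of first administration of study treatment to 30 days after the date of the last actual administration". SAP section 7 carries the same restriction ("Safety summaries (tables, figures) include only data from the on-treatment period") but never defines the period, so the programmer has only the protocol rule.

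Two things fall outside the restriction. Deaths have their own table: "a separate summary for death including on treatment and post treatment deaths will be provided". Listings carry no such limit: "ISST-Plus score data will be listed by treatment, subject and visit/time; abnormalities will be flagged". For the ISST-Plus tables the protocol says: "Summary statistics will be provided by treatment and visit/time as appropriate".

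The endpoints run longer than the window. Protocol Table 2-1 lists "InterSePT Scale for Suicidal Thinking-Plus (ISST-Plus) score at baseline, day 29, day 57, day 85, and day 115 or last visit" and sets adverse events as an endpoint over the whole study. Protocol 9.1.1 asks subjects who stop treatment to keep attending, naming days 85 and 115 in particular, and 9.1.3 encourages them to stay in the trial.

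The treatment has no fixed administration dates. Protocol 6.1 says that subjects can "access PEAR-004 as needed to receive suggestions about coping strategies". Use is planned for 12 weeks, and a footnote to Table 8-1 has app data collected from day 1 to day 85.

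**The concern.** The plan collects safety data to day 115 for everyone who attends, including subjects who have stopped treatment, and then applies a rule that can remove those data from every between-arm summary. ISST-Plus is the trial's prospective suicidality measure, and protocol 10.2.1 requires it at every visit. The scores removed would be those of subjects who stopped early, who are the subjects the retrieved-dropout policy is meant to keep in view.

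The arms could also be affected differently. PEAR-004 offers therapeutic content, whereas the sham shows only a timer after a notification. If sham use stops earlier, sham subjects have shorter windows. Adverse events are tabulated as numbers and percentages of subjects with no stated adjustment for window length, so the percentages would then not be directly comparable.

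**Working it through.** The documents state no figure for this point, so there is none to reproduce. The check is date arithmetic.

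**Inputs.** Window end is last administration + 30 days (protocol 12.5.2). Post-baseline ISST-Plus visits are on days 29, 57, 85 and 115 (Tables 2-1 and 8-1). Planned use is 12 weeks (protocol section 3). App data collection runs to day 85 (Table 8-1 footnote). Visits are to be held as near the planned day as possible, with no numeric window (section 8).

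**Rule.** Let L be the study day of last administration. A visit on day v is summarised only if v ≤ L + 30, that is, L ≥ v − 30.

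| Visit | Earliest L that keeps it |
|---|---|
| Day 29 | 29 − 30 = −1, so always kept |
| Day 57 | 57 − 30 = 27 |
| Day 85 | 85 − 30 = 55 |
| Day 115 | 115 − 30 = 85 |

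With on-schedule visits, L of 55 to 84 therefore loses day 115. L of 27 to 54 loses days 85 and 115. L of 1 to 26 loses days 57, 85 and 115.

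**Completers.** Twelve weeks is 12 × 7 = 84 days. If administration ends on day 84, the window ends on 84 + 30 = 114 and an on-schedule day-115 visit is lost for everyone. If day-85 use counts, the window ends on 85 + 30 = 115 and the visit is kept, with no day to spare.

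**Share lost at an on-schedule day 115, if administration means use and day-85 use is possible.** The loss is 1 − q, where q is the share using the app on day 85. The documents do not give q, so I take a range. The upper value borrows the only daily-use figure available, 87.5% of days in the one-month open-label trial of the precursor app.

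| q (assumed) | Share lost |
|---|---|
| 0.25 | 75% |
| 0.50 | 50% |
| 0.75 | 25% |
| 0.875 | 12.5% |

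**Visit timing.** For an end-of-study visit o days from day 115, L must be at least 85 + o. If access ends on day A and use is independent from day to day with probability q, the chance of keeping the visit is 1 − (1 − q)^k, with k = A − (85 + o) + 1, or 0 if that is negative. Averaging over o from −3 to +3, equally likely (assumed), for q from 0.25 to 0.875:

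- A = 84: 18% to 41% kept.
- A = 85: 28% to 55% kept.

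A visit after day 115 is lost for everyone whose last administration is by day 85. A visit on day 114 is kept after last administration on day 84.

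**Formal stoppers.** A subject who stops on day 50 has a window ending on 50 + 30 = 80. Days 85 and 115 are lost from the summaries even if the subject attends both.

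**Unequal windows (illustration).** Last use on day 50 in one arm and day 85 in the other gives adverse event windows of 80 and 115 days. The first is 80/115 = 70% of the second.

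**The case against.** The strongest reply is that administration need not mean opening the app. Access is by prescription code, a timer shows the remaining availability, notifications go out whether or not the app is opened, and discontinuation is a separate act by the subject or investigator. If administration means active access through day 85, on-schedule completers keep day 115 and mere non-use removes nothing. That reading is open, although the word *actual*, and the plan in 6.6.1 to record frequency of use, lean towards last use. It does not remove the problem. The result still turns on whether access ends on day 84 or day 85, and subjects who formally stop early still lose summarised data from 30 days after stopping.

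A reader might infer that almost everyone loses the day-115 score, or that the rule cannot produce the endpoint. The documents do not support either. Day 115 is exactly day 85 + 30, the same 30 days appear in SAE reporting (10.1.3), and a visit held a little early can be kept after an earlier last use. A reader might also infer that all later safety data disappear. They do not: loss begins 30 days after last administration, affects only tables and figures, and leaves the listings and the death summary intact. Listings do not, however, give a between-arm summary of a stated endpoint.

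A treatment-emergent window of 30 days after treatment is a coherent choice for an exposure-based adverse event table. That stands, and is a reason to keep it as a supplementary table. The difference in use between arms is a possibility, not a finding. The precursor app's engagement figures are high, but they say nothing about the sham.

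**Conclusion.** The point holds as a conflict between a stated analysis rule and stated endpoints. Under any definition of administration, a subject whose last administration is before day 85 drops out of the day-115 ISST-Plus summary if the visit is on schedule. Before day 55 the day-85 summary is lost too, and before day 27 the day-57 summary.

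How many subjects this touches cannot be fixed from the documents. It depends on the missing definition, on when access ends and on actual visit dates. For on-schedule visits it is 100% if administration ends by day 84. On the last-use reading with use possible on day 85, it is 12.5% to 75% over the assumed range of day-85 use. If administration means access through day 85, it is confined to those who stop early. Unequal adverse event windows follow only if duration of use differs between arms, but the plan has no safeguard if it does.

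**What to change.** In protocol 12.5.2 and SAP section 7:

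- Summarise ISST-Plus and vital signs at all scheduled visits through the end-of-study visit, whatever the date of last app use.
- Summarise adverse events and SAEs from day 1 through the end-of-study visit or last contact, on the same basis.
- Define last actual administration for both PEAR-004 and the sham, and put the definition in the SAP, which has none.
- Keep the window of last administration + 30 days for a supplementary treatment-emergent adverse event table.

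No new data are needed, because Table 8-1 already records ISST-Plus, vital signs, adverse events and SAEs in the database at day 115. The cost is a short edit to each document and one extra table. The small downside is that some events long after last use enter the main table, which the supplementary table lets the reader see.
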